3.7. Summary

Although smoking rates have declined in the overall US population, there has been little to no decline among people with ADs. A nicotine reduction strategy for combustible tobacco combined with e-cigarette availability may have complementary effects on smoking reductions and consequent tobacco-related health effects in this vulnerable population. This research is highly significant because it will model how the availability of e-cigs, a non-combusted nicotine product that is rapidly increasing in use among US smokers, impacts the effectiveness of a reduced-nicotine policy for cigarettes in this vulnerable population. It is responsive to the goals of the FDA in that the study conditions are designed to model real-world scenarios of possible harm reduction policies in a population that is vulnerable to smoking persistence.

4. Project Study Methods

This study will use a four-condition, parallel-groups research design. After a baseline period in which daily smoking rate and other baseline assessments are completed, participants will be randomly assigned to one of the following four conditions for a 16-week experimental period: (1) normal nicotine content cigarettes (NNCCs, 15.8 mg/g) alone, which serves as the control condition; (2) very low nicotine content cigarettes (VLNCCs, 0.4 mg/g) alone; (3) VLNCCs + tobacco-flavored nicotinized e-cigs (TF e-cig, 4.8 - 5.0% nicotine by weight, NBW, if they choose to use the Vuse or JULL devise, respectively); or (4) VLNCCs + preferred-flavor nicotinized e-cigarette (PF e-cig).

5. Study Screening Procedures

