The research assistant will review the entire screening assessment battery for initial eligibility determination, confirming the participant meets the above described inclusion/exclusion criteria. All eligibility criteria that are not related to physiological measurements will be assessed during the first portion of the screening visit, and all criteria related to physiological measurements will be determined during the second portion of the screening. The final eligibility of the participant will be determined by a licensed medical professional (MD, DO, NP, PA, Master's prepared RN or CRN) at each site after reviewing the Medical History Questionnaire, BDI, Mini Neuropsychiatric Interview, and the MINI suicide subscale. The licensed medical professional may meet with a participant if available and think it necessary for eligibility determination. He/she will sign off on eligibility prior to the first baseline visit. If the licensed medical professional determines the participant is not medically eligible to participate in the study, has current symptomatology that would interfere with interpretation of the data, or is unlikely to complete the study he/she will inform the research assistants who will contact the participant prior to the first baseline visit. The licensed medical professional will not need to review the medical history forms of participants who are ineligible for other, non-medical reasons.

If a participant fails the urine or saliva toxicology screen due to a prescription medication he/she is taking, then he/she will not be automatically excluded. The interviewer will make note of this when he/she submits the forms to the licensed medical professional for final eligibility determination.

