All participants will also be asked to select their top three flavors of e-cigarette liquid from a list read to them by the RA. This question will be asked in preparation for giving flavored pods to participants who are randomized into the flavored e-cigarette condition. This information will be recorded directly into REDCap. Participants will be asked to rate these top three flavors based on either previous experience with these flavors or to indicate how much they believe that they will like or dislike the flavors.

Physiological measures collected at Baseline 2 will be entered directly into REDCap by the interviewer:

- 1) CO
- 2) Blood Pressure
- 3) Heart Rate
- 4) Body temperature
- 5) Oxygen saturation
- 6) Respiratory rate
- 7) Urine or Saliva Toxicology
- 8) Urine Pregnancy (if applicable; to be performed every two weeks)

The following assessments will be administered as an interview at Baseline 2 and then entered directly into REDCap by the interviewer:

- 1) Concomitant Medications Form

- 2) Health Changes Questionnaire
- 3) Time Since Last Cigarette Questionnaire

The following assessments will be administered at Baseline 2 and completed by the participant directly in REDCap:

- 1) BDI
- 2) OASIS
- 3) COVID19 Symptom Questionnaire
- 4) Respiratory Symptom Questionnaire
- 5) MNWS
- 6) WISDM
- 7) PANAS
- 8) QSU (usual brand)
- 9) Vaping Craving Questionnaire
- 10) CES (usual brand)
- 11) Vaping Evaluation Scale
- 12) CPT (usual brand)
- 13) Snaith-Hamilton Pleasure Scale (SHAPS)
- 14) E-Cigarette flavor rating questionnaire
 - a. Participants will rate only the flavors that they received from staff for this visit

In the event that the REDCap website is not functioning, the assessments will be administered aloud and participant answers will be recorded securely. The interviewer will enter the data into REDCap when it resumes functioning properly. This information should be recorded in the 'End of Visit Evaluation Form'.

- 1) for each picture as they appear on the screen.

6.3 E-cigarette Training Session (Baseline 2):

Participants assigned to an e-cig condition will be told that they will be provided with a JUUL. If a participant indicates an unwillingness to use the JUUL device, the research assistants will offer the participant the Vuse Solo as alternative device. If the participants does not wish to use either device, he or she would be ineligible for the study.

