Participants in the e-cigarette conditions will be given e-cigarette pods BEFORE the training session occurs. These pods will be either picked up at the lab (preferred) or delivered to the participant 1 to 2 days before their Baseline 2 visit occurs. Participants randomized to the e-cigarette conditions will be notified before their Baseline 2 visit (but after the 7-day period following Baseline 1) and informed of their e-cigarette condition. Participants randomized to the flavored condition will be given pods of up to three flavors of their choice. Staff will calculate how many total pods participants will be given at this time based on their smoking rate, and participants will be able to choose the proportion of each flavor that they would like to receive.

The e-cigarette training session will occur over video chat after the physiological measurements have been collected. The first 30 minutes of the training session will consist of the participant being taught how to use, charge, and replace pods/cartridges for their e-cigarette of choice. Participants will first try their JUUL using the tobacco flavor, and then decide which device they would like to use for the duration of the study. If desired, participants are able to choose a preferred device to use without testing both e-cigarettes. At this point, participants who are in the tobacco-only flavor condition will conclude their training session.

For all visits following Baseline 2, participants in the preferred flavor condition are permitted

to take up to three flavors home per week, but can choose to take less than three flavors if desired. Participants will take home their chosen pods or cartridges of up to three flavors until next visit. Participants will be able to change their flavors at only one point in the study if they desire. Participants will only be allowed to take home three flavors at one time. Participants will be given an E-cigarette instructional manual that reviews the e-cigarette training done at this visit. Participants will be encouraged to call with any device issues.

6.4. Interactive Voice Response System:

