At the end of the first baseline visit, participants will be trained to use the Interactive Voice Response (IVR) System, which will contact participants each day throughout the study and ask about their smoking behavior as well as withdrawal symptoms the week before and after Baseline 2. We will also review the IVR adherence incentive program, which consists of \$1 per call plus a \$10 bonus for seven consecutive calls.

The IVR system is operated by TeleSage (<https://telesage.com/about/>). To be enrolled in the IVR system, research staff will enter the participant's initials, telephone number, subject identifier, and visit dates into the IVR TCORS website. Identifying information (initials and telephone numbers) will not be extracted as part of the data by the bioinformatics group. Please refer to TeleSage's privacy statement and HIPAA compliance form for additional information.

Baseline 2 biological specimens:

1) Urine sample for smoking biomarker assessment:

Participants will be asked to provide a urine sample (first void of the day) at the second baseline session and to post-randomization weeks 8 and 16 for biomarker assessment. Biomarker analysis will provide nicotine and carcinogen exposure outcome measures and verify compliance with VLNC cigarettes. Samples will be stored at -80C. Urine samples will be analyzed for total nicotine (cotinine plus its glucuronide conjugate, a useful measure of daily nicotine exposure), the tobacco-specific nitrosamine 4-methylnitrosamineo-1-(3-pyridyl)-1-butanol (NNAL), and metabolites of 4 polycyclic aromatic hydrocarbons (PAHs), which are biomarkers of tobacco smoke carcinogens and decrease upon tobacco cessation or reduction. Anatabine is a minor alkaloid that is reduced in users of VLNC cigarettes and e-cigs. Therefore, anatabine levels in samples from those assigned to the VLNCC, VLNCC +TF e-cig and VLNCC+PF e-cig conditions should be lower than levels from those in the NNCC condition. These analyses will be performed by the [name] lab at the University of Minnesota.

2) Saliva Samples for smoking biomarker assessment:

We will collect a saliva sample at the second baseline session and post-randomization weeks 8 and 16 for analysis of nicotine metabolite ratio (NMR; ratio of 3-hydroxycotinine [3 HC] to cotinine [COT]), a phenotypic marker of nicotine metabolic rate. Analyses of these samples will be performed by the [name] lab.

Biomarker shipping and storage:

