Data will be stored locally at each site. Long-term storage of all study data, for at least 7 years after study completion, will be at the University of Vermont.

12. Adverse Events

The research assistant will ask about adverse events at each session, using a form that assesses the nature, severity, duration, action taken, and outcome of study-related adverse events. AEs will be captured from the time of first study cigarette. Participants will be given contact cards to inform us of events that occur between study contacts. Any AE that remains open will be reviewed and closed at an interview conducted 30 days after the study completion date (completers) or when the study should have ended had the participant completed the study (dropouts and those withdrawn by investigator).

All procedures will be monitored to ensure that they conform to the approved protocol. In addition, monitoring will be done of all unforeseen circumstances that might arise and affect safety; of all reports of serious adverse events as defined in 38 CFR 46 (death, new or prolonged hospitalization, persistent or significant disability/incapacity); of other significant adverse events (adverse events that lead to drop out by the participant or termination by the investigator); of unexpected adverse events resulting from the study, and of expected adverse events.

Any SAE will be brought to the attention of the site PIs as soon as possible and not longer

than 24 hours. Any AE or SAE that is both unexpected and related to study participation will be reported to the IRB within 7 days of the event. The local IRB will make a determination as to whether additional reporting requirements are needed. IRB actions will be reported to the funding agency by the PIs no less than annually and more frequently as recommended by the local IRB. Any SAEs will be summarized in the yearly Progress Reports to the funding agency, including a review of frequency and severity. All SAEs will be followed through ongoing consultation with the physician caring for the patient until they resolve, result in death, or stabilize and are not expected to improve. The study staff will be in close contact with participants and health care providers throughout the study to monitor for potential unanticipated problems. Any unanticipated problems will be discussed at the weekly research staff meetings and reported as required to the local IRB.

13. Withdrawal or Monitoring of Participants

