8) If a participant is discharged from or discontinues his or her methadone or buprenorphine treatment, they will be discontinued from the study.

The following will be monitored and can lead to the participant being withdrawn by the PI or Licensed Medical Professional:

- 1) Cigarettes per day increase: Continued participation will be evaluated by the site PI if the average number of cigarettes per day (CPD) increases by more than 100% from the average CPD during baseline as determined by CPD at Baseline 2.
- 2) Blood pressure (BP) or heart rate (HR) changes: If any of the following occur post-enrollment: 1) BP is at or above 160/100 or below 90/50, or 2) HR is at or above 115 bpm or below 45 bpm a manual blood pressure and heart rate measurement will be taken after 10 minutes have passed. If the manual reading is still out of range, a 'Blood Pressure and Heart Rate Symptom Checklist' and 'Medical Event Form' will be completed, and the participant will be monitored by the medical professional.
- 3) Expired breath Carbon Monoxide increase: If the average of two consecutive CO measurements meets the criteria below then the 'Medical Event Form' will be completed and the participant will be monitored by the medical professional.
 - a. CO is greater than 50 ppm if CO at Baseline 1 is <20 ppm.
 - b. CO is greater than 60 ppm if CO at Baseline 1 is 20 – 34 ppm.
 - c. CO is greater than 70 ppm if CO at Baseline 1 is 35 – 49 ppm.
 - d. CO is greater than 80 ppm if CO at Baseline 1 is 50 – 64 ppm.
 - e. CO is greater than 90 ppm if CO at Baseline 1 is 65 – 80 ppm.
- 4) Any hospitalization or debilitation in which participation in the study could be detrimental to the recovery process. This will be self-reported by the participant and will be reviewed by the site PI and medical professional to determine whether continued participation in the study is appropriate.
- 5) If a participant is behaving in an inappropriate or threatening manner, admits to lying about eligibility criteria, is participating in other smoking research studies that could affect the primary outcome measures, etc., then the PI can withdraw him/her from the study at the PI's discretion.
- 6) If a participant fails to attend regularly scheduled research assessment visits or comply with the research procedures or schedule, then the PI can withdraw him/her from the study at the PI's discretion.

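### Section 6.3 makes randomised people who decline both e-cigarette devices ineligible, in arms 3 and 4 only, which conflicts with the intent-to-treat rule in 9.1

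*Combined protocol and SAP*

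**What the plan says.** Section 6.3 opens with the people concerned: "Participants assigned to an e-cig condition will be told that they will be provided with a JUUL". Vuse Solo is offered to anyone unwilling to use JUUL. Then: "If the participants does not wish to use either device, he or she would be ineligible for the study". The same section places this after assignment and disclosure: "Participants randomized to the e-cigarette conditions will be notified before their Baseline 2 visit". Section 8.1 confirms that the e-cigarette conditions are not blinded.

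The eligibility criteria in 5.6 contain nothing on willingness to use a device. Section 5.7 has the licensed medical professional complete eligibility much earlier: "He/she will sign off on eligibility prior to the first baseline visit".

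Section 9.1 applies intent-to-treat to all analyses, by assigned condition and irrespective of compliance. Section 5.2 counts 53 randomised per condition on that basis. For missing data, 9.1 uses all available data without imputation if they are missing at random.

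**The concern.** A person who declines both devices is a randomised participant who does not take up the assigned product. Section 9.1 keeps such people in the analysis; section 6.3 calls them ineligible. The two sections cannot both be followed as they stand.

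The rule is one-sided. Arms 1 and 2 receive no device, so nobody there can be removed by it. The nearest rule covering every arm, in section 13, is discretionary: for a participant who does not "comply with the research procedures or schedule, then the PI can withdraw him/her from the study".

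The rule also acts at Baseline 2, before any post-baseline CPD exists. If decliners' data stop there, arms 3 and 4 consist of device acceptors while arms 1 and 2 still contain people who would have declined. Comparisons across that line could be biased, including the planned linear trend and the contrast of normal-nicotine cigarettes with the two e-cigarette arms. The trial's stated goal is to model the availability and appeal of e-cigarettes, so smokers who decline an available device are part of the answer.

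**Working it through.** **Reading the sections together**

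- *Timing.* Section 4 says: "After a baseline period in which daily smoking rate and other baseline assessments are completed, participants will be randomly assigned". Section 6.3 has randomisation before Baseline 2. These differ, but on either reading the device rule acts after assignment.
- *Follow-up.* Section 6.4 describes the IVR system, "which will contact participants each day throughout the study and ask about their smoking behavior", but does not say whether someone ruled ineligible is still in the study. Section 12 schedules a contact 30 days after the study ended or "when the study should have ended had the participant completed the study (dropouts and those withdrawn by investigator"), but only to close open adverse events. No section provides CPD follow-up for decliners.
- *Contrast within the protocol.* Section 7.7 keeps participants in weekly visits during a quit attempt and accepts a later decision to stop e-cigarettes. Only refusal at Baseline 2 leads to ineligibility.

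**The plan's sample size (section 9.2)**

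Effect size 0.60, two-sided alpha 0.05 and 80% power give 44.59 by the two-sample t-test, rounded up to 45 evaluable per arm. With 15% loss, 45/0.85 = 52.9, so 53. The stated figure reproduces. Power with 45 per arm is 80.4%.

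**Effect of losing decliners**

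Assumptions, none from the documents:
- refusal share r of 2–20% in arms 3 and 4, which is 2 to 21 of 2 × 53 = 106 people;
- decliners differ from acceptors by δ = 0.3 to 1.0 SD in Week 16 CPD.

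An arm's true mean is r × (decliner mean) + (1 − r) × (acceptor mean). Dropping decliners therefore shifts arms 3 and 4 by r × δ.

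Evaluable numbers are 45, 45, 45(1 − r), 45(1 − r); the last two are 44, 43, 40 and 36 at r = 2%, 5%, 10% and 20%. Type I error comes from the noncentral t with N − 4 degrees of freedom.

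Linear trend, weights −3, −1, 1, 3, at r = 10% and δ = 1.0:
- contrast shift = (1 + 3) × 0.10 = 0.40;
- standard error = √(9/45 + 1/45 + 1/40 + 9/40) = 0.687;
- noncentrality = 0.40/0.687 = 0.58, giving 8.9%.

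| Refusal | δ = 0.3 | δ = 0.5 | δ = 1.0 |
|---|---|---|---|
| 2% | 5.0% | 5.0% | 5.2% |
| 5% | 5.1% | 5.3% | 6.0% |
| 10% | 5.4% | 6.0% | 8.9% |
| 20% | 6.3% | 8.7% | 20.3% |

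For normal-nicotine cigarettes against the two e-cigarette arms (weights −1, 0, 0.5, 0.5), the range over the same grid is 5.0% to 18.2%.

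**With the baseline-CPD covariate of 9.1**

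Assume a baseline–outcome correlation of 0.5. The gap in residual SD is δ × (1 − share explained by baseline)/√(1 − 0.25). Linear trend at δ = 1.0:

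| Refusal | Baseline explains all | Half | None |
|---|---|---|---|
| 10% | 5.0% | 6.3% | 10.3% |
| 20% | 5.0% | 10.0% | 25.5% |

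The 25.5% needs the highest refusal, the largest gap and no help from baseline, all at once.

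**The case against.** The strongest reply is that 6.3 says who continues and 9.1 says how randomised people are analysed. A protocol can end participation and still analyse as assigned: section 13 withdraws people immediately for several events under the same intent-to-treat rule. No section says that decliners leave the analysis or that their data stop. That last point is true, and the bias figures depend on it. But the section 13 withdrawals can occur in any arm, whereas 6.3 reaches two arms only and acts before a single post-baseline CPD value exists. Analysis as assigned means little for people with no outcome data.

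Refusal may also be rare. Section 3.3 cites high acceptability of e-cigarettes among smokers with mental health conditions, and all 18 people in the team's pilot completed it. Everyone chooses flavours at Baseline 1, and a second device is offered. These are not refusal rates, and the pilot's participants were asked to switch to an e-cigarette from the outset, but they do point to the low end of the range. At 5% refusal and a 0.5 SD gap the trend test runs at 5.3% unadjusted and 5.1% if baseline explains half the gap.

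The no-imputation rule applies only if data are missing at random, and the end of 9.1 is a fragment, so a rule for other cases may not be visible. That stands as a limit, though no analysis rule recovers outcomes that were never collected. Drop-out rate is already a secondary endpoint in section 17, which covers part of the reporting but not the status of decliners.

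**Conclusion.** The concern holds: the sentence in 6.3 is wrong as written. It is an automatic exclusion after randomisation, it can act only in arms 3 and 4, and it contradicts 9.1. The outcome follow-up of the people affected is not described.

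The size and direction of any bias are unknown, because the documents give neither a refusal rate nor a decliner–acceptor difference. The inflation figures assume that data collection stops at Baseline 2, which the word ineligible implies but no section states. On that assumption the effect is negligible at about 2% refusal, modest at 10%, and serious only near 20% with a large gap that baseline CPD does not explain. The point should be fixed; confidence is medium because the refusal rate is unknown. The sample size of 53 per condition is not in question.

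**What to change.** Delete the ineligibility sentence from 6.3. State in 6.3 and 9.1 that randomised participants who decline both devices remain in the existing daily IVR calls and weekly visits, are analysed in their assigned arm, and are reported by arm.

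The sponsor must also reconcile section 4 with 6.3 on when randomisation occurs. Once decliners are retained, it must settle how 6.3, 7.7 and 8.2 apply to their product supply: 8.2 supplies e-cigarettes to everyone in those arms, and 7.7 addresses declining them only in a quit attempt.

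An optional trade-off is to ask everyone about device willingness before randomisation and apply the answer to all four arms. This narrows the population, and later decliners would still stay in the intent-to-treat analysis.

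*Cost.* Text edits and the supply decision; no new assessment. Payments under 7.9 for Weeks 1–16 are up to 16 × $100 + 15 × $20 + $150 = $2,050 per person before IVR payments. That is $4,100 for 2 people and $43,050 for 21, plus staff time.

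Retention dilutes the e-cigarette effect, as intent-to-treat intends. If decliners gain nothing from e-cigarettes, a 0.60 SD difference between an e-cigarette arm and arm 2 becomes 0.60 × (1 − r):

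| Refusal | Effect if retained | Power, retained | Power, dropped |
|---|---|---|---|
| 2% | 0.59 | 78.8% | 79.9% |
| 10% | 0.54 | 71.7% | 77.9% |
| 20% | 0.48 | 61.5% | 75.5% |

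With no refusal, power is 80.4%. At low refusal the cost is slight.
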